5.4 IMMEDIATE REPORTING REQUIREMENTS FROM INVESTIGATOR TO SPONSOR

Certain events require immediate reporting to allow the Sponsor to take appropriate measures to address potential new risks in a clinical study. The investigator must report such events to the Sponsor immediately; under no circumstances should reporting take place more than 24 hours after the investigator learns of the event. The following is a list of events that the investigator must report to the Sponsor within 24 hours after learning of the event, regardless of relationship to study drug:

- Serious adverse events (see Section 5.4.2 for further details)
- Adverse events of special interest (see Section 5.4.2 for further details)
- Pregnancies (see Section 5.4.3 for further details)

The investigator must report new significant follow-up information for these events to the Sponsor immediately (i.e., no more than 24 hours after becoming aware of the information). New significant information includes the following:

- New signs or symptoms or a change in the diagnosis
- Significant new diagnostic test results
- Change in causality based on new information
- Change in the event's outcome, including recovery
- Additional narrative information on the clinical course of the event

Investigators must also comply with local requirements for reporting serious adverse events to the local health authority and IRB/EC.

5.4.2 Reporting Requirements for Serious Adverse Events and Adverse Events of Special Interest

5.4.2.1 Events That Occur prior to Study Drug Initiation

After informed consent has been obtained but prior to initiation of study drug, only serious adverse events caused by a protocol-mandated intervention should be reported. For reports of serious adverse events and adverse events of special interest, investigators should record all case details that can be gathered immediately (i.e., within 24 hours) on the Adverse Event eCRF and submit the report via the Serious Adverse Event/Adverse Event of Special Interest Reporting Form.

The Serious Adverse Event/Adverse Event of Special Interest Reporting Form and Fax Coversheet should be completed and faxed or e-mailed immediately (i.e., no more than 24 hours after learning of the event), as follows. Ensure that information is also entered in the EDC system.

[contact]
E-mail: [contact]

5.4.2.2 Events That Occur after Study Drug Initiation

After initiation of study drug, serious adverse events and adverse events of special interest will be reported until 90 days after the last dose of study drug or until they receive another anti-cancer therapy, whichever comes first. After initiation of study drug, all adverse events will be reported until 30 days (see guidance and table in Section 5.3.1) after the last dose of study drug. Investigators should record all case details that can be gathered immediately (i.e., within 24 hours after learning of the event) on the Adverse Event eCRF and submit the report via the Serious Adverse Event/Adverse Event of Special Interest Reporting Form.

The Serious Adverse Event/Adverse Event of Special Interest Reporting Form provided to investigators should be completed and submitted to the Sponsor or its designee immediately (i.e., no more than 24 hours after learning of the event), either by faxing or by scanning and e-mailing the form with use of the fax number or e-mail address provided to investigators. All information will also need to be entered and submitted via the EDC system.

Instructions for reporting post-study adverse events are provided in Section [5.6](#).

5.4.3 Reporting Requirements for Pregnancies

5.4.3.1 Pregnancies in Female Patients

Female patients of childbearing potential will be instructed to immediately inform the investigator if they become pregnant during the study or within 5 months after the last dose of study drug. A paper Clinical Trial Pregnancy Reporting Form should be completed and faxed or e-mailed immediately as follows below (i.e., no more than 24 hours after learning of the event).

[contact]
Email: [contact]

Pregnancy should not be recorded on the Adverse Event eCRF or the Serious Adverse Event/Adverse Event of Special Interest Reporting Form. The investigator should discontinue all study treatment and counsel the patient, discussing the risks of the pregnancy and the possible effects on the fetus. Monitoring of the patient should continue until conclusion of the pregnancy. Any serious adverse events associated with the pregnancy (e.g., an event in the fetus, an event in the mother during or after the pregnancy, or a congenital anomaly/birth defect in the child) should be reported on the Serious Adverse Event/Adverse Event of Special Interest Reporting Form and Adverse Event eCRF. In addition, the investigator will submit a Clinical Trial Pregnancy Reporting Form when updated information on the course and outcome of the pregnancy becomes available.

5.4.3.2 Abortions

A spontaneous abortion should be classified as a serious adverse event (as the Sponsor considers abortions to be medically significant), recorded on the Adverse Event eCRF, and reported to the Sponsor or designee immediately via the Serious Adverse Event/Adverse Event of Special Interest Reporting Form (i.e., no more than 24 hours after learning of the event; see Section [5.4.2](#)).

If a therapeutic or elective abortion was performed because of an underlying maternal or embryofetal toxicity, the toxicity should be classified as a serious adverse event, recorded on the Adverse Event eCRF, and reported to the Sponsor immediately (i.e., no more than 24 hours after learning of the event; see Section [5.4.2](#)). A therapeutic or elective abortion performed for reasons other than an underlying maternal or embryofetal toxicity is not considered an adverse event.

All abortions should be reported as pregnancy outcomes on the paper Clinical Trial Pregnancy Reporting Form.

5.4.3.3 Congenital Anomalies/Birth Defects

Any congenital anomaly/birth defect in a child born to a female patient exposed to study drug should be classified as a serious adverse event, recorded on the Adverse Event eCRF and reported to the Sponsor or designee immediately via the Serious Adverse Event/Adverse Event of Special Interest Reporting Form (i.e., no more than 24 hours after learning of the event; see Section 5.4.2).

5.5 FOLLOW-UP OF PATIENTS AFTER ADVERSE EVENTS

5.5.1 Investigator Follow-Up

The investigator should follow each adverse event until the event has resolved to baseline grade or better, the event is assessed as stable by the investigator, the patient is lost to follow-up, or the patient withdraws consent. Every effort should be made to follow all serious adverse events considered to be related to study drug or study-related procedures until a final outcome can be reported.

During the study period, resolution of adverse events (with dates) should be documented on the Adverse Event eCRF and in the patient's medical record to facilitate source data verification.

All pregnancies reported during the study should be followed until pregnancy outcome. If the EDC system is not available at the time of pregnancy outcome, follow reporting instructions provided in Section 5.4.3.1.

5.5.2 Sponsor Follow-Up

For serious adverse events, adverse events of special interest, and pregnancies, the Sponsor or a designee may follow-up by telephone, fax, electronic mail, and/or a monitoring visit to obtain additional case details and outcome information (e.g., from hospital discharge summaries, consultant reports, autopsy reports) in order to perform an independent medical assessment of the reported case.

5.6 ADVERSE EVENTS THAT OCCUR AFTER THE ADVERSE EVENT REPORTING PERIOD

After the end of the adverse event reporting period (see Section 5.3.1), all deaths, regardless of cause, should be reported through use of the Survival Follow-Up eCRF. In addition, if the investigator becomes aware of a serious adverse event or adverse event of special interest that is believed to be related to prior study drug treatment or study procedure, the event should be reported through use of the Adverse Event eCRF.

5.7 EXPEDITED REPORTING TO HEALTH AUTHORITIES, INVESTIGATORS, INSTITUTIONAL REVIEW BOARDS, AND ETHICS COMMITTEES

The Sponsor will promptly evaluate all serious adverse events and adverse events of special interest against cumulative product experience to identify and expeditiously communicate possible new safety findings to investigators, IRBs, ECs, and applicable health authorities based on applicable legislation.

To determine reporting requirements for single adverse event cases, the Sponsor will assess the expectedness of these events with use of the following reference documents:

- Atezolizumab Investigator's Brochure
- Local prescribing information for BCG (OncoTICE)

The Sponsor will compare the severity of each event and the cumulative event frequency reported for the study with the severity and frequency reported in the applicable reference document.

Reporting requirements will also be based on the investigator's assessment of causality and seriousness, with allowance for upgrading by the Sponsor as needed.

6. STATISTICAL CONSIDERATIONS AND ANALYSIS PLAN

All analyses will be performed by cohort. Selected analyses may also be performed for all cohorts combined as specified below.

All patients treated with any amount of study drug (atezolizumab or BCG) will be included in all analyses unless specified otherwise.

Analyses of DLTs will be performed on an ongoing basis as described in Section 3.1. Analyses of endpoints related to anti-tumor activity will be performed periodically among patients with sufficient follow-up. Final analyses will be performed after the LPLV has occurred.

Continuous variables will be summarized using means, SDs, medians, and ranges. Categorical variables will be summarized by proportions. The baseline value of any variable will be defined as the last available value prior to the first administration of study treatment.

6.1 DETERMINATION OF SAMPLE SIZE

The sample sizes for Cohorts 1A, 2, and 3 were based on clinical and operational considerations. The sample size for Cohort 1B was based on a 3+3 dose de-escalation design appropriate for assessing DLTs and MTD or MAD of BCG in combination with atezolizumab.

An evaluation of results from Cohorts 1A and 1B will be performed prior to initiation of enrollment in Cohorts 2 and 3. [Table 11](#) shows the 95% CI for selected observed CR rates for a range of sample sizes for Cohorts 1A and 1B pooled.

Table 11 95% CI for Selected Observed 6-Month Complete Response Rates in Cohorts 1A and 1B

Cohort	N	Number of Patients with CR (Observed CR Rate)	95% CI for CR Rate ^a
Cohorts 1A and 1B pooled	12	5 (42%)	(15%, 72%)
		6 (50%)	(21%, 79%)
	15	6 (40%)	(16%, 68%)
		7 (47%)	(21%, 73%)
	20	8 (40%)	(19%, 64%)
		9 (45%)	(23%, 68%)

CR = complete response.

^a Clopper-Pearson method.

[Table 12](#) shows the 95% CI for selected observed CR rates with the planned maximum enrollment of patients in either Cohorts 2 or 3.

Table 12 95% CI for Selected Observed 6-Month Complete Response Rates with the Planned Maximum Enrollment of Patients in Either Cohort 2 or 3

Cohort	N	Number of Patients with CR (Observed CR rate)	95% CI for CR Rate ^a
Cohorts 2 or 3	20	10 (50%)	(27%, 73%)
		12 (60%)	(36%, 81%)
		14 (70%)	(46%, 88%)
		16 (80%)	(56%, 94%)
		18 (90%)	(68%, 99%)

CR = complete response.

^a Clopper-Pearson method.

6.2 SUMMARIES OF CONDUCT OF STUDY

Enrollment, major protocol deviations including major deviations of inclusion/exclusion criteria, and reasons for discontinuation from the study will be summarized by cohort and among pooled cohorts for the treated population. Study treatment administration and reasons for discontinuation from the study treatment will be summarized by cohort and among pooled cohorts for all treated patients.

6.3 SUMMARIES OF TREATMENT GROUP COMPARABILITY

Demographic variables such as age, sex, race/ethnicity, baseline characteristics (e.g., prior therapy, time since initial diagnosis, site[s] of disease, number of site[s], EORTC risk score, smoking status, and ECOG performance status) will be summarized by cohort and among pooled cohorts for all treated patients.

6.4 EFFICACY ANALYSES

6.4.1 Primary Efficacy Endpoint

The primary efficacy outcome measure for this study is CR at 6 months after the start of study treatment as assessed by the investigator on the basis of cystoscopic assessment and urine cytology. The CR rate will be summarized by timepoint for each cohort, and the corresponding 95% CI will be calculated on the basis of the Clopper-Pearson method.

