3.1.2 Study Procedures for All Cohorts

Patients will be required to provide sample tumor tissue showing the presence of CIS, to be obtained within 60 days prior to study entry. Tissue should be submitted as formalin-fixed paraffin-embedded (FFPE) blocks (blocks preferred) or at least 10 unstained slides, with an associated pathology report, for central testing. Patients with fewer than 10 unstained slides available at baseline (but no fewer than five) may be eligible following discussion with the Medical Monitor. The Sponsor may replace patients who are later found to be unevaluable for tumor PD-L1 expression by central testing.

Tumor response assessment via cystoscopy and urine cytology will occur every 12 weeks for the first 2 years, and every 24 weeks thereafter until 5 years, and then yearly.

A mandatory tissue biopsy will be obtained from all patients 6 months after C1D1 of atezolizumab. For patients in Cohort 1A, biopsies should be obtained up to 21 days prior to atezolizumab administration. For patients in Cohorts 1B, 2, and 3, biopsies should be obtained 14–21 days prior to BCG intravesical instillation (e.g., Weeks 10, 22, 46, 70 and 94; see [Appendix 3](#)).

The Sponsor may replace patients who are discontinued from the study before the required tumor biopsy samples are obtained.

At the 6-month timepoint (Week 24 visit), documentation of a complete response (CR) is required to continue on study treatment.

Definition of Complete Response (must meet all 3 criteria):

- Cytology: not positive (see below)
- Upper Urinary Tract Imaging (if performed): normal, or abnormal but supportive of CR (with non-positive selective ureteral cytologies)

- Cystoscopy: bladder appears normal; or bladder appears abnormal but all biopsies are negative; or any grade papilloma, any grade papillary urothelial neoplasm of low malignant potential (PUNLMP), or low grade pTa

Interpretation of Urine Cytology:

- If results are Unsatisfactory, Atypical Cell, Suspicious, or Indeterminate, then assay must be repeated no less than 24 hours and up to 21 days later.
- If the results are again Unsatisfactory or Atypical Cell (2 in a row), then treat as if the result was negative.
- Two consecutive Suspicious or Indeterminate urine cytology specimens require further evaluation by cystoscopy and/or upper tract imaging as deemed appropriate by the investigator

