- If cytology results are Suspicious or Indeterminate and the biopsies are negative, then treat as if the result was negative
- All occurrences of positive urine cytology will require further evaluation by cystoscopy and/or upper tract imaging. A positive cytology result only indicates presence of disease and cannot be used alone to determine disease progression.

The date of a positive cytology result can be used for the date of recurrence, if the results of the cystoscopy, biopsy, or upper urinary tract assessment shows recurrence.

Patients with persistent and/or recurrent high grade NMIBC without progression (stage or grade progression of active disease, or the presence of new disease) at 12 weeks from treatment initiation may continue on study treatment.

Patients with recurrent low-grade papillary disease will be required to undergo resection with TURBT (unless medically contraindicated) and may continue on study and receive study treatment.

Indications for Discontinuation from Study for Disease Progression

- Stage or grade progression at any timepoint would require discontinuation from study therapy.
- Patients with persistent and/or recurrent high-grade NMIBC (any pT1, high grade pTa, or CIS) on or after the 6-month biopsy will be discontinued from study treatment and offered the option to undergo cystectomy or other bladder-sparing modalities as is clinically appropriate. Patients who undergo cystectomy will be requested to submit additional tissue from their cystectomy specimens.
- Patients with evidence of disease progression to muscle-invasive or metastatic disease at any timepoint will be discontinued from study treatment.

For all patients, additional evaluation (imaging, exam under anesthesia, biopsies) should be performed at investigator discretion for any of the following circumstances:

- Abnormal cystoscopy
- Positive urine cytology
- Two sequential suspicious or indeterminate urine cytology specimens

Study treatment with atezolizumab may be continued for a maximum of 32 q3w cycles or a total of 96 weeks of therapy. BCG treatment (induction and maintenance) may be continued for a maximum of 120 weeks (as clinically indicated; see [Appendix 3](#)). All study treatment will be discontinued in patients who undergo cystectomy or experience disease recurrence/progression or unacceptable toxicity, and in those who are not benefiting from study treatment (in the opinion of the investigator or the patient).

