3.4.7 Rationale for the Collection of Tumor Specimens on Treatment and at Recurrence/Disease

The assessment of immunomodulation and PD-L1/PD-1 pathway inhibition in tumor tissue may guide selection of the appropriate dose and exposure for atezolizumab in combination BCG for future studies. Biopsy samples will be collected for the study of PD changes related to the additive or synergistic effects of atezolizumab and BCG (changes in PD-L1 and infiltration of CD8+ T cells and other exploratory biomarkers). The timing of on-treatment biopsy was selected to allow assessment of potential synergistic effect

of atezolizumab and BCG (following BCG induction) as well as to assess CR, disease recurrence, and/or disease progression (optional) and to allow adequate healing after biopsy and prior to the next BCG administration. A biopsy at tumor recurrence/progression will enable the evaluation of the role of immune and tumor type-related, as well other exploratory biomarkers (including but not limited to T-cell markers and tumor mutation status) associated with disease progression.

The presence of disease at 3 months after initiation of BCG induction has been shown to be predictive for disease recurrence and disease progression (Solsona et al. 2000; Sylvester et al. 2006); however, the use of maintenance BCG has been shown to increase response rates between 3 and 6 months. Therefore, 6 months is the recommended timepoint for disease response assessment (Lamm et al. 2000; Jarow et al. 2014).

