3.5.4 Efficacy Outcome Measures

The primary efficacy outcome measure for this study is as follows:

- CR at the 6-month evaluations after the start of study treatment. Patients must be evaluated for CR by both cystoscopy and cytology and bladder biopsies will be required for the 6-month CR disease assessment.

The secondary efficacy outcome measures for this study are as follows:

- CR at the 3-month disease assessment, evaluated by both cystoscopy and cytology.
- Duration of CR, defined as time from first occurrence of a documented CR until the time of recurrence of NMIBC or death from any cause
- RFS rate at 6, 12, and 18 months, defined as the proportion of patients who are alive and free of persistent/recurrent high-risk NMIBC
- Bladder-intact DFS, defined as time from first study treatment to earliest evidence of progression to muscle-invasive disease in the bladder, regional pelvic progression, distant metastasis, bladder cancer–related death, or cystectomy or death from any cause
- PFS, defined as the time from first study treatment to the first occurrence of progression to muscle-invasive disease or death from any cause
- CFS, defined as the time from first study treatment to cystectomy or death from any cause
- Overall survival, defined as the time from first study treatment to death from any cause

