4.5.5 Tumor and Response Evaluations

Screening and tumor response assessment will be in accordance with national (EAU AUA, and NCCN) guidelines, which recommend cystoscopic examination and urine cytology every 12 weeks for the first 2 years, and every 24 weeks thereafter (or as clinically appropriate) until 5 years, and then yearly. Upper tract imaging with CT urography or intravenous pyelogram will be performed at the 6- and 18-month disease assessments. Annual upper tract imaging thereafter is recommended as clinically indicated.

Screening assessments must include imaging of the upper tract collecting system, which may include any one or more of the following: intravenous pyelogram, CT urography, renal ultrasound with retrograde pyelogram, ureteroscopy, or magnetic resonance imaging urogram. Pelvic CT before TURBT may be considered, but is not required.

Primary assessment of tumor (at screening and while on study) will be with cystoscopy and urine cytology.

White-light cystoscopy, narrow band imaging cystoscopy, or fluorescent (blue-light) cystoscopy will be acceptable for baseline assessment. The same methodology used to assess disease sites at screening should be used throughout the study except when medical contraindicated (e.g., the same cystoscopy protocol and urine examination).

The Sponsor may replace patients who have had a change in the type of cystoscopy (e.g., screening with white-light cystoscopy and follow-up evaluation with blue-light cystoscopy) to ensure consistent evaluation over time. All known sites of disease must be documented at screening and re-assessed at each subsequent tumor evaluation. A Bladder Map template ([Appendix 11](#)) has been provided and should be used to document the approximate size and location of abnormalities observed at screening, baseline, and on study cystoscopy/TURBT assessments.

Mandatory bladder biopsies will be performed at the 6-month tumor assessment. In absence of visible tumor, template biopsies should be obtained from all quadrants of the bladder. Template biopsies may be performed under anesthesia, at the discretion of the investigator. Regions of the template biopsies should include the trigone, left lateral wall, right lateral wall, posterior wall, and dome. Where feasible, the same evaluator should perform assessments if possible to ensure internal consistency across visits.

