At the investigator's discretion, cystoscopy and/or urine cytology may be repeated at any time if progressive or recurrent disease is suspected.

At the 6 month timepoint (24 week visit), documentation of a complete response (CR) is required to continue on study treatment.

Definition of Complete Response (must meet all 3 criteria):

- Cytology: not positive (see below)
- Upper Urinary Tract Imaging (if performed): normal, or abnormal but supportive of CR (with non-positive selective ureteral cytologies)
- Cystoscopy: bladder appears normal; or bladder appears abnormal but all biopsies are negative; or any grade papilloma, any grade PUNLMP, or low grade pTa

Interpretation of Urine Cytology:

- If results are Unsatisfactory, Atypical Cell, Suspicious, or Indeterminate, then assay must be repeated no less than 24 hours and up to 21 days later
- If the results are again Unsatisfactory or Atypical Cell (2 in a row), then treat as if the result was negative
- Two consecutive Suspicious or Indeterminate urine cytology specimens require further evaluation by cystoscopy and/or upper tract imaging as deemed appropriate by the investigator
- If cytology results are Suspicious or Indeterminate and the biopsies are negative, then treat as if the result was negative
- All occurrences of positive urine cytology will require further evaluation by cystoscopy and/or upper tract imaging. A positive cytology result only indicates presence of disease and cannot be used alone to determine disease progression.

The date of a positive cytology result can be used for the date of recurrence, if the results of the cystoscopy, biopsy, or upper urinary tract assessment shows recurrence.

Patients with persistent and/or recurrent high grade NMIBC without progression (stage or grade progression of active disease, or presence of new disease) at 12 weeks from treatment initiation may continue on study treatment. to muscle-invasive disease.

Patients with recurrent low-grade papillary disease will be required to undergo resection with TURBT (unless medically contraindicated) and may continue on study and receive study treatment.

Indications for Discontinuation from Study Treatment for Disease Progression

- Stage or grade progression at any timepoint would require discontinuation from study therapy.

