- Patients with persistent and/or recurrent high-grade NMIBC (any pT1, high grade pTa, or CIS) on or after the 6-month biopsy will be discontinued from study treatment and offered the option to undergo cystectomy or other bladder-sparing modalities as is clinically appropriate. Patients who undergo cystectomy will be requested to submit additional tissue from their cystectomy specimens.
- Patients with evidence of disease progression to muscle-invasive or metastatic disease at any timepoint will be discontinued from study treatment.

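### The 6-month CR definition does not say that CIS on a mandatory template biopsy rules out a complete response when the bladder looks normal

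*Combined protocol and SAP*

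**What the plan says.** The parts of the plan that bear on 6-month CR do not agree about biopsy.

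- **Outcome measure (Synopsis and Section 3.5.4).** CR is evaluated by cystoscopy and cytology, and "bladder biopsies will be required for the 6-month CR disease assessment". The 3-month CR in the same list rests on cystoscopy and cytology only. Section 3.4.7 gives assessment of CR as one reason for the timing of the on-treatment biopsy.
- **CR criteria (Sections 3.1.2 and 4.5.5, same list).** All three must be met: cytology not positive; upper tract imaging, if done, normal or consistent with CR; and a cystoscopy criterion that begins "Cystoscopy: bladder appears normal; or bladder appears abnormal but all biopsies are negative" and goes on to allow papilloma, PUNLMP and low-grade pTa. Biopsy also enters the cytology rules: "If cytology results are Suspicious or Indeterminate and the biopsies are negative, then treat as if the result was negative".
- **Biopsy procedure (Section 4.5.5).** Biopsies are mandatory at 6 months. "In absence of visible tumor, template biopsies should be obtained from all quadrants of the bladder".
- **Treatment rules.** Section 3.1.2: "At the 6-month timepoint (Week 24 visit), documentation of a complete response (CR) is required to continue on study treatment". Under Section 4.5.5, patients with persistent or recurrent high-grade disease, CIS included, "on or after the 6-month biopsy will be discontinued from study treatment". Section 4.6.2 has the same stopping rule.
- **Analysis (Section 6.4.1).** The primary endpoint is "CR at 6 months after the start of study treatment as assessed by the investigator on the basis of cystoscopic assessment and urine cytology", reported with a Clopper-Pearson 95% CI.
- **RFS (Section 6.4.2).** The 6-month rate counts patients who are alive without persistent or recurrent high-grade NMIBC.

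**The concern.** The normal-appearance branch of the cystoscopy criterion carries no biopsy condition, and nothing elsewhere says that a positive template biopsy removes a CR. Section 6.4.1, from which the primary analysis will be programmed, omits the biopsies that Section 3.5.4 requires. One patient could therefore be a success on the primary endpoint and a failure on 6-month RFS at the same assessment. Because CR is investigator-assessed at roughly 10 to 20 sites, such patients could also be classified differently from site to site.

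The case is not far-fetched. Every patient must have CIS at entry, and Section 1.1.1 notes that CIS is hard to detect with standard cystoscopy. Template biopsies are taken precisely when nothing is visible.

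The 6-month CR rate in pooled Cohorts 1A and 1B is the efficacy figure tabulated in Section 6.1, beside the evaluation made before Cohorts 2 and 3 open.

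**Working it through.** **1. One patient under each rule.** Take a patient at 6 months with a normal-looking bladder, non-positive cytology, acceptable upper tract imaging and CIS on template biopsy.

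| Rule | Result for this patient |
|---|---|
| CR criteria, Sections 3.1.2 and 4.5.5 | All three met: CR |
| Primary endpoint basis, Section 6.4.1 | Cystoscopy and cytology clear: CR |
| CR needed to continue treatment, Section 3.1.2 | Met on the literal criteria |
| Outcome measure, Synopsis and Section 3.5.4 | Biopsy required, but no required result is stated |
| Stopping rules, Sections 4.5.5 and 4.6.2 | Persistent CIS: stop treatment |
| 6-month RFS, Section 6.4.2 | Failure |

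Histology is used in three places in the criteria: the abnormal-appearance branch, the list of tolerated low-grade lesions, and the rule for Suspicious or Indeterminate cytology. None of them applies to this patient.

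**2. Reproducing the plan's intervals.** For x responders among n patients, the exact limits are:

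- lower = 0.025 quantile of Beta(x, n − x + 1)
- upper = 0.975 quantile of Beta(x + 1, n − x)

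All 11 intervals in Tables 11 and 12 reproduce after rounding to whole percent, so the tables contain no numerical error.

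**3. Effect of one misclassified patient.** The shift in the CR rate is 1/n. At n = 12, 15 and 20, the two rows of Table 11 differ by exactly one patient. The n = 10 row is not in the plan's tables; it is the planned size of Cohort 2 or Cohort 3 before expansion.

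| n | Shift (1/n) | Lower count, 95% CI | One more CR, 95% CI |
|---|---|---|---|
| 10 | 10.0 points | 4/10: 12.2% to 73.8% | 5/10: 18.7% to 81.3% |
| 12 | 8.3 points | 5/12: 15.2% to 72.3% | 6/12: 21.1% to 78.9% |
| 15 | 6.7 points | 6/15: 16.3% to 67.7% | 7/15: 21.3% to 73.4% |
| 20 | 5.0 points | 8/20: 19.1% to 63.9% | 9/20: 23.1% to 68.5% |

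**4. Illustration for several patients.** The documents give no frequency of CIS found only on biopsy. The number reclassified from CR to non-CR is therefore an assumption, shown from 0 to 3.

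| Reclassified | Starting from 8/20 | Starting from 5/12 |
|---|---|---|
| 0 | 40.0% (19.1% to 63.9%) | 41.7% (15.2% to 72.3%) |
| 1 | 35.0% (15.4% to 59.2%) | 33.3% (9.9% to 65.1%) |
| 2 | 30.0% (11.9% to 54.3%) | 25.0% (5.5% to 57.2%) |
| 3 | 25.0% (8.7% to 49.1%) | 16.7% (2.1% to 48.4%) |

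**The case against.** The strongest reply is that the plan uses cystoscopy as shorthand for the whole examination, tissue included. The cystoscopy criterion itself contains biopsy results and histologic diagnoses. Section 6.4.2 bases PFS on cystoscopy and cytology, although muscle invasion is a histologic finding. Appendix 3 describes the mandatory 6-month biopsy in the footnote to the cystoscopy and cytology row. On this usage, Section 6.4.1 does not exclude biopsy. Requiring biopsies for the CR assessment and then ignoring the result would make no sense, and CIS is not among the tolerated lesions. The bare normal-appearance branch may exist only because the same definition serves visits without mandatory biopsies, such as 3 months.

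This supports the view that non-CR is intended. It does not supply the rule. The CR criterion separates how the bladder looks from what biopsies show. Section 3.5.4 adds biopsies to cystoscopy and cytology at 6 months but not at 3 months, which would be redundant if cystoscopy already included them.

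It can also be said that an investigator holding a pathology report of CIS is unlikely to record a CR, that sites are trained on the eCRF, and that a mismatch would show up in the RFS rate and the reasons for stopping treatment. These points lower the likelihood of error, though the training material cannot be checked here. Finally, a shift of 1/n per patient is true of any misclassification in a small cohort, and Cohorts 2 and 3 open on a benefit-risk judgment rather than a CR cut-off. Both statements are correct and limit the weight of the point.

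**Conclusion.** The concern holds and should be fixed. Followed as written, the CR rule counts a patient with biopsy-proven CIS as a primary-endpoint success, while the stopping rules and the RFS definition treat the same finding as persistent disease. The likely intent is non-CR, so this is a drafting inconsistency and not a decision to disregard biopsy.

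The error runs in one direction, upward, by the 1/n shifts shown above for each affected patient. The total effect is unknown and could be zero, because the number of affected patients is not given. The plan states no hypothesis test and no CR threshold, so the consequence is a possibly inflated descriptive estimate and inconsistent classification between endpoints and sites, not a change in any error rate.

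**What to change.** - **Sections 3.1.2 and 4.5.5:** add that at the 6-month assessment CR also requires no high-grade disease (CIS, high-grade pTa or any pT1) on the mandatory bladder biopsies, whatever the cystoscopic appearance. Leave the definition for other visits as it is.
- **Section 6.4.1:** name cystoscopic assessment, urine cytology and the mandatory 6-month bladder biopsies as the basis of the primary endpoint.
- **Missing biopsies:** since the biopsy result becomes part of the definition, state how a missing or inadequate 6-month biopsy is classified. Counting it as non-CR is the conservative choice.
- **Optional:** a sensitivity analysis of 6-month CR by cystoscopy and cytology alone.

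The cost is wording only, because the biopsies are already mandatory. The reported 6-month CR rate may be lower.
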